# 1 Protocol Summary

Title	The ENROUTE Transcarotid Neuroprotection System (ENROUTE Transcarotid NPS) DW-MRI Evaluation.
Objective	To correlate pre and post procedure DW-MRI for patients treated with the transcarotid artery revascularization (TCAR) procedure.
Design	This is a prospective, single-arm, multi-center evaluation of patients requiring carotid revascularization who are treated with the FDA-cleared ENROUTE Transcarotid NPS in conjunction with the FDA-approved ENROUTE Transcarotid Stent.
Enrollment	A minimum of 50 patients and a maximum of 75.
Locations	Up to 10 sites in the United States of America and up to 2 sites in the European Union.
Primary Endpoint	Incidence of ipsilateral new white lesions by DW-MRI post procedure.
Secondary Endpoints	
The following secondary endpoints will be assessed 0 to 30 days:
 

▪ All Stroke

▪ Neurological Death

▪ Stroke/Death in patients eligible for ROADSTER 2

• Volume of DW-MRI lesions

• Location of DW-MRI Lesions

• Stroke/Death in patients ineligible for ROADSTER 2

• Rate of contralateral new white lesions by DW-MRI

Patient Population	Symptomatic or Asymptomatic patients with atherosclerotic extracranial internal carotid stenosis (ICA) with or without involvement of the contiguous common artery (CCA).
Planned Schedule	
First patient enrolled: November 2018
 
Last patient enrolled: November 2019
 
Last 30-day follow-up visit: December 2019

## 3 Introduction

Cerebral embolization during carotid artery stenting (CAS) can often precipitate severe adverse neurological effects. Most major clinical studies of CAS have used distal filters (from a transfemoral route) for cerebral protection and have compared the neurologic complication rates with those of carotid endarterectomy (CEA). The contemporary absolute stroke/death rates for CEA and filter-protected CAS within a tightly proscribed randomized trial are low (2.3% versus 4.4%) (CREST). To power a trial to compare the impact of procedural and/or technical modifications (such as improved embolic protection strategies) would require several thousand patients at the minimum. New white lesions on DW-MRI of the brain occur at a much higher rate than stroke and death. Many of these lesions remain clinically covert but the impact on cognition in the long term is unknown. The ICSS sub-study revealed a 50% new white lesion rate following transfemoral CAS (which rose to 73% for filter-protected transfemoral CAS) compared with 17% for CEA. Although the incidence of new DW-MRI lesions is far higher than the incidence of clinically apparent neurological deficits. In the ICSS MRI subset, the DW-MRI lesions with the largest volume were significantly associated with the occurrence of neurologic events. Although the fate and clinical relevance of these lesions remain

unknown, their incidence makes them an attractive surrogate to maintain adequate power whilst reducing the size of the study population.

## 4 Device Overview and Usage

The ENROUTE Transcarotid Neuroprotection System (NPS) was 510(k) cleared by the FDA on February 9, 2015, and the ENROUTE Transcarotid Stent System was PMA Approved by FDA on May 18, 2015. Both devices are commercially available in the United States. The ENROUTE Transcarotid Neuroprotection System was granted the CE marking of conformity on January 27, 2016. The ENROUTE Transcarotid Stent System was granted the CE marking of conformity on July 2, 2013.

### 4.1 Device Description

#### The ENROUTE Transcarotid Stent System

[figure not shown]
The Silk Road ENROUTE Transcarotid Stent System consists of a nitinol self-expanding stent preloaded on a 5F (.065" / 1.65 mm) or 6F (.078" / 1.98 mm) sheathed delivery system. The rapid exchange delivery system consists mainly of an inner shaft and an outer sheath with radiopaque markers, and a Tuohy Borst valve. The inner shaft consists of a support member and wire lumen. The proximal portion of the support member is comprised of a hub connected to a stainless steel wire and hypotube and distally of a stainless steel coil. The wire lumen originates distally in a catheter tip and terminates proximally at a guidewire exit port designed to accept a .014" (0.36 mm) guidewire. The outer sheath has a proximal shaft and distal outer sheath with a nominal working length of 57 cm. The self-expanding ENROUTE Transcarotid Stent System is constrained within the space between the inner shaft and the distal outer sheath, located between distal and proximal stent markers on the inner shaft. The stent expands to its unconstrained diameter when released from the deployment catheter into the carotid artery. Upon deployment, the stent forms a lattice to cover the diseased arterial segment and to push outward on the luminal surface, helping to maintain the patency of the artery. Due to the self-expanding behavior of nitinol, the stents are indicated for placement into vessels that are 1-2 mm smaller in diameter than the unconstrained diameter of the stent. Device depictions and components are provided in Figure 1. The ENROUTE Transcarotid Stent (nitinol implant) is available in 18 sizes mounted on delivery systems in two (2) crossing profiles depending on stent diameter (unconstrained). Refer to Table 1.

Non-clinical testing has demonstrated that the ENROUTE Transcarotid Stent is MR Conditional. A patient with this device can be scanned safely in an MR system meeting the following conditions:

- Static magnetic field of 1.5-Tesla or 3-Tesla, only
- Maximum spatial gradient magnetic field of 4,000 Gauss/cm (40 Tesla/m) or less
- Maximum MR system reported, whole body averaged specific absorption rate (SAR) of 2-W/kg (Normal Operating Mode).

Under the scan conditions defined above, the ENROUTE Transcarotid Stent is expected to produce a maximum temperature rise of 2.4°C after 15 minutes of continuous scanning. In non-clinical testing, the image artifact caused by the device extends approximately 5 mm from the ENROUTE Transcarotid Stent when imaged with a gradient echo pulse sequence and a 3-Tesla MRI system. The artifact does obscure the device lumen.

**Figure 1. ENROUTE Transcarotid Stent System**

1. Tuohy Borst valve  
 2. Hypotube  
 3. Coil  
 4. Catheter Inner Shaft Tip  
 5. Inner Shaft Hub  
 6A. Proximal Shaft  
 6B. Distal Outer Sheath  
 7. Outer Sheath Luer Hub  
 8. Pod Housing Crimped Stent  
 9. Tuohy Borst Y-Connection  
 10. Proximal Inner Shaft Marker (Stop)  
 11. Outer Sheath Radiopaque Marker  
 12. Proximal Valve End  
 13. Distal Inner Shaft Stent Marker  
 14. Coil Sleeve  
 15. Wire Lumen  
 16. Guidewire Exit Port

**Table 1. ENROUTE Transcarotid Stent and Delivery System Dimensions**

ENROUTE CODES	UNCONSTRAINED STENT DIMENSIONS Diameter x Length (mm)	CROSSING PROFILE
SR-0520-CS	5 x 20	5F (.078", 1.98mm)
SR-0530-CS	5 x 30	5F (.078", 1.98mm)
SR-0540-CS	5 x 40	5F (.078", 1.98mm)
SR-0620-CS	6 x 20	5F (.078", 1.98mm)
SR-0630-CS	6 x 30	5F (.078", 1.98mm)
SR-0640-CS	6 x 40	5F (.078", 1.98mm)
SR-0720-CS	7 x 20	5F (.078", 1.98mm)
SR-0730-CS	7 x 30	5F (.078", 1.98mm)
SR-0740-CS	7 x 40	5F (.078", 1.98mm)
SR-0820-CS	8 x 20	5F (.078", 1.98mm)
SR-0830-CS	8 x 30	5F (.078", 1.98mm)
SR-0840-CS	8 x 40	5F (.078", 1.98mm)
SR-0920-CS	9 x 20	6F (.087", 2.21mm)
SR-0930-CS	9 x 30	6F (.087", 2.21mm)
SR-0940-CS	9 x 40	6F (.087", 2.21mm)
SR-1020-CS	10 x 20	6F (.087", 2.21mm)
SR-1030-CS	10 x 30	6F (.087", 2.21mm)
SR-1040-CS	10 x 40	6F (.087", 2.21mm)

### The ENROUTE Transcarotid Neuroprotection System (NPS)

The ENROUTE Transcarotid Neuroprotection System (NPS) consists of three primary components: the Transcarotid Arterial Sheath, the Flow Controller, and the Venous Return Sheath. When assembled, the ENROUTE Transcarotid NPS creates an arteriovenous shunt that reverses the flow of blood at the treatment site of the carotid arteries from antegrade to retrograde due to the pressure gradient between arterial and venous pressure thereby shunting embolic particles away from the cerebral circulation. The rate of reverse flow (low or high) through the arteriovenous shunt is regulated by the Flow Controller. Subsequent iterations of the ENROUTE Transcarotid Neuroprotection System (NPS) may be used during this study.

## **4.2 Intended Use**

### **4.2.1 ENROUTE Transcarotid Stent**

The ENROUTE Transcarotid Stent System used in conjunction with the ENROUTE Transcarotid Neuroprotection System is indicated for the treatment of patients at high risk for adverse events from carotid endarterectomy, who require carotid revascularization and meet the criteria outlined below.

- Patients with neurological symptoms and  $\geq 50\%$  stenosis of the common or internal carotid artery by ultrasound or angiogram OR patients without neurological symptoms and  $\geq 80\%$  stenosis of the common or internal carotid artery by ultrasound or angiogram, AND
- Patients must have a vessel diameter of 4-9 mm at the target lesion, AND
- Carotid bifurcation is located at minimum 5 cm above the clavicle to allow for placement of the ENROUTE Transcarotid Neuroprotection System.

### **4.2.2 ENROUTE Transcarotid Neuroprotection System**

The ENROUTE® Transcarotid Neuroprotection System is intended to provide transcarotid vascular access, introduction of diagnostic agents and therapeutic devices, and embolic protection during carotid artery angioplasty and stenting procedures for patients diagnosed with carotid artery stenosis and who have the appropriate anatomy described below:

- Adequate femoral venous access
- Patients must have a vessel diameter of 6 mm of the common carotid artery and is free of significant disease at the access point, AND
- Carotid bifurcation is located at minimum 5 cm above the clavicle to allow for placement of the ENROUTE Transcarotid Neuroprotection System.

## **5 Objective**

The goal of this evaluation is to document the incidence of post procedure DW-MRI lesions (relative to baseline) in patients treated with the transcarotid artery revascularization (TCAR) procedure.

## **6 Design**

This is a prospective, single-arm, multi-center evaluation of patients requiring carotid revascularization who are treated with the FDA-cleared ENROUTE Transcarotid NPS in conjunction

with the FDA-approved ENROUTE Transcarotid Stent System. Both the ENROUTE Transcarotid NPS and ENROUTE Transcarotid Stent System have received CE mark and are commercially available in the European Union.

## 7 Endpoints

### 7.1 Primary Endpoint

Incidence of ipsilateral new white lesions by DW-MRI 30 days post procedure.

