### 10.2 Diffusion-Weighted Magnetic Resonance Imaging (DW-MRI) Evaluation

A DW-MRI evaluation is to be done pre, post and 30 days post the index procedure. The following sequences should be used for each evaluation.

Magnetic resonance using a 3 Tesla MR imaging scanner. Sequences : T1, T2, T2\*, GRE, FLAIR, DWI and ADC map. Slice thickness: 4mm

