**Table 1. DW-MRI visit windows**

Visit Window	Imaging Timing
Pre-procedure	≤ 72 hours prior to procedure
Post-procedure	Within 12 – 60 hours post procedure
30 days Post-procedure	30 days(-7/+15 days) post procedure

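### Section 7.1 ties the primary endpoint to the day-30 DW-MRI, so a diffusion reading would understate procedural lesions to the extent that their signal has faded, although a 12–60 hour scan is already scheduled

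*Protocol*

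**What the plan says.** Section 7.1 gives the primary endpoint as "Incidence of ipsilateral new white lesions by DW-MRI 30 days post procedure". The Protocol Summary (Section 1) gives it without a day: "Incidence of ipsilateral new white lesions by DW-MRI post procedure".

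Section 10.2 plans three examinations: "A DW-MRI evaluation is to be done pre, post and 30 days post the index procedure". Table 1 of that section (DW-MRI visit windows) gives the two later scans separate rows. The row named post-procedure is timed "Within 12 – 60 hours post procedure", and the row named 30 days post-procedure is timed "30 days(-7/+15 days) post procedure". The sequences at every examination are "T1, T2, T2\*, GRE, FLAIR, DWI and ADC map".

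The purpose is stated in two places. The Introduction (Section 3) opens with embolization during carotid stenting and adopts new DW-MRI lesions as a surrogate because they are far more frequent than stroke or death. It cites comparison rates: "The ICSS sub-study revealed a 50% new white lesion rate following transfemoral CAS", 73% with filter protection, and 17% for endarterectomy. It does not say when those scans were taken. Section 5 sets the goal as the incidence of lesions after the procedure compared with baseline, with no restriction to day 30.

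Section 14 plans no hypothesis test, so the trial reports estimated rates with exact confidence intervals.

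**The concern.** The wording in Section 7.1 matches the label of the late scan, and nothing in the protocol says that a lesion seen at 12–60 hours counts toward the primary endpoint. Bright diffusion signal marks a recent infarct and fades with time. A patient with an embolic lesion from the procedure could therefore be positive on the early scan, negative on diffusion at day 30, and scored as free of new lesions.

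This goes beyond the difference in wording between Sections 1 and 7.1. A sponsor could reconcile the two by copying day 30 into the summary. The protocol would then be consistent, but its primary reading would still fit its purpose poorly.

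What is at stake is interpretation. With no test planned, the primary rate is the trial's main finding, and the Introduction has already placed 17%, 50% and 73% before the reader. A low rate could be taken as evidence of neuroprotection when part of it is loss of signal.

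**Working it through.** **Which scan Section 7.1 points to.** The late window runs from 30 − 7 = day 23 to 30 + 15 = day 45. The early window ends at 60 hours, which is day 2.5. The two do not overlap, and the reference to 30 days in Section 7.1 fits only the late one.

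**Inputs for size.** The protocol gives no power, precision or sample-size derivation to reproduce, and no figure for how long diffusion signal lasts. The inputs are:
- *p*, the true share of patients with a new procedural lesion on the early scan. The values 17% and 50% are borrowed from the Introduction as illustrations only.
- *v*, the share of those patients still diffusion-positive on days 23–45. This is an assumption, shown over a range.
- *n* = 50, the minimum enrollment in Section 9.

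**Patient-level loss.** Recorded rate = *p* × *v*. This counts procedural lesions only and sets lesions arising later to zero.

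| *v* | true 17% recorded as | true 50% recorded as |
|---|---|---|
| 0 | 0% | 0% |
| 0.10 | 1.7% | 5% |
| 0.25 | 4.3% | 12.5% |
| 0.50 | 8.5% | 25% |
| 0.75 | 12.8% | 37.5% |
| 1 | 17% | 50% |

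**Several lesions per patient.** If a positive patient has *m* lesions and each persists independently with probability *q*, the recorded rate is *p* × [1 − (1 − *q*)^*m*]. With *m* = 3:
- *q* = 0.10: 17% × (1 − 0.90³) = 4.6%; 50% becomes about 13.5%.
- *q* = 0.25: 17% × (1 − 0.75³) = 9.8%; 50% becomes 28.9%.
- *q* = 0.50: 17% × (1 − 0.50³) = 14.9%; 50% becomes 43.8%.

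More than half of positive patients are lost only if *q* < 0.50 with one lesion, *q* < 1 − 0.5^(1/2) = 0.29 with two, or *q* < 1 − 0.5^(1/3) = 0.21 with three.

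**What the interval would show.** Exact 95% intervals at *n* = 50, with *v* = 0.25 at day 30 and counts rounded to whole patients:
- True 17%: the early reading gives about 8/50 (7.2% to 29.1%); day 30 gives about 2/50 (0.5% to 13.7%).
- True 50%: the early reading gives about 25/50 (35.5% to 64.5%); day 30 gives about 6/50 (4.5% to 24.3%), which excludes the true 50%.

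The confidence interval reflects sampling error only. It gives no warning of lost signal.

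**The case against.** The strongest reply is that Section 7.1 need not mean a diffusion reading of the late scan alone.

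- *Cumulative reading.* The endpoint could mean incidence through day 30, which would include the early scan. This is possible but weaker. Section 7.2, directly below, writes out an interval from day 0 to day 30 when it means one, and Section 7.1 does not.
- *Meaning of DW-MRI.* Section 10.2 lists FLAIR and T2 within the DW-MRI evaluation, and Section 19.1 leaves the reading method to core laboratory guidelines. A day-30 reader might therefore pick up the residue of an early lesion on those sequences. This stands as a possibility, and it is why the size above is confined to a diffusion reading. Section 7.1 itself does not provide for it.
- *No decision depends on the rate.* No comparison is planned, and the early scan is required and goes to the core laboratory. This also stands. The information is collected and can be reported, so the trial does not lose its ability to address its objective. What is badly fixed is which reading carries the name of primary endpoint.

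A reader might go further and infer that the day-30 scan misses most procedural lesions. The documents give no persistence figure, and the calculation shows that the answer turns on it and on the number of lesions per patient. A reader might also infer that the lesions counted at day 30 would mostly not be procedural. That needs a rate of late lesions, and the protocol gives none. Nor do the volume, location and contralateral endpoints share the problem as written, since Section 7.2 already assesses them from day 0 to day 30.

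**Conclusion.** The concern holds in a limited form. On its most natural reading, Section 7.1 takes the primary endpoint from the day 23–45 scan, which is a poor match for an endpoint motivated by embolization during the procedure. If diffusion signal fades over weeks, a diffusion reading at that time understates the procedural lesion rate, by an amount the documents cannot settle. For patient-level persistence from 0 to 0.75, a true 50% would be recorded as 0 to 37.5% and a true 17% as 0 to 12.8%. There is no loss if persistence is complete, and less loss where patients have several lesions.

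Three assumptions carry this: the fading itself, the persistence range, and a day-30 reading made on diffusion alone. Lesions arising after the procedure are set to zero in the arithmetic; any that occur would add to the day-30 count without being procedural. The direction of the bias for procedural lesions needs only that persistence is incomplete. Because this is the primary endpoint and the repair is cheap, it should be corrected.

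**What to change.** In Sections 1 and 7.1, use one definition: new ipsilateral DWI lesions on the 12–60 hour scan relative to the pre-procedure scan. Then state the role of the day-30 examination:
- use the FLAIR and T2 images already acquired to report whether the early lesions persist;
- report any DWI-positive lesion first seen at day 30 separately, as a late lesion;
- state that a negative day-30 DWI does not cancel a lesion seen at 12–60 hours.

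The core laboratory reading instructions should say the same. The cost is protocol wording and those instructions; no scan, sequence or patient is added. The downside for the sponsor is that the reported primary rate will probably be higher than a day-30 diffusion reading would give.

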### 7.2 Secondary Endpoints

The following secondary endpoints will be assessed 0 to 30 days:

- All Stroke
- Neurological Death
- Volume of DW-MRI lesions
- Location of DW-MRI Lesions
- Stroke/Neurological Death in patients eligible for ROADSTER 2
- Stroke/Neurological Death in patients ineligible for ROADSTER 2
- Rate of contralateral new white lesions by DW-MRI

## 8 Population

Patients participating in this evaluation will be comprised of male and female symptomatic or asymptomatic patients requiring carotid revascularization.

### 8.1 Patient Eligibility

Patients must meet ALL of the inclusion criteria to be considered for the study. If ANY of the exclusion criteria are met, the patient cannot be enrolled in this study or treated using the study devices.

Note: Patients treated with TCAR within the ROADSTER 2 Post Approval Study are eligible to participate in this evaluation since this evaluation only adds non-invasive imaging before and after a routine TCAR procedure. ROADSTER 2 only excludes patients who are participating in ***investigational*** device or drug studies and does not preclude the enrollment of patients subjected to other routine medical care.

### 8.2 Inclusion Criteria

1. Patient must meet one of the following criteria regarding neurological symptom status and degree of stenosis:

**Symptomatic:** Stenosis must be  $\geq 50\%$  as determined by ultrasound or angiogram^1 and the patient has a history of stroke (minor or non-disabling; NIHSS  $\leq 4$  or mRS  $\leq 2$ ), TIA and/or amaurosis fugax within 180 days of the procedure ipsilateral to the carotid artery to be stented.

**OR**

**Asymptomatic:** Stenosis must be  $\geq 80\%$  as determined by ultrasound or angiogram without any neurological symptoms within the prior 180 days.

 For this protocol, this is limited to CT angiogram.

2. Target vessel must meet diameter requirements for stent (refer to stent IFU for diameter requirements).
3. Patient has a discrete lesion located in the internal carotid artery (ICA) with or without involvement of the contiguous common carotid artery (CCA).
4. Patient is willing to comply with the protocol requirements and return to the treatment center for all required clinical evaluations.
5. Patient must have a life expectancy  $\geq$  3 years at the time of the index procedure without contingencies related to other medical, surgical or endovascular intervention.
6. Patient meets at least one of the surgical high-risk criteria listed in CMS National Coverage Determination (NCD) for Percutaneous Transluminal Angioplasty (20.7)

### **8.3 Exclusion Criteria**

Each potential patient must be screened to ensure that they do not meet any of the following exclusion criteria. This screening is to be based on known medical history and data available at the time of eligibility determination and enrollment.

1. Patient has an alternative source of cerebral embolus, including but not limited to:
  - a. Patient has chronic atrial fibrillation.
  - b. Patient has had any episode of paroxysmal atrial fibrillation within the past 6 months, or history of paroxysmal atrial fibrillation requiring chronic anticoagulation.
  - c. Knowledge of cardiac sources of emboli. e.g. left ventricular aneurysm, intracardiac filling defect, cardiomyopathy, aortic or mitral prosthetic heart valve, calcific aortic stenosis, endocarditis, mitral stenosis, atrial septal defect, atrial septal aneurysm, or left atrial myxoma).
  - d. Recently (<60 days) implanted heart valve (either surgically or endovascularly), which is a known source of emboli as confirmed on echocardiogram.
  - e. Abnormal angiographic findings: ipsilateral intracranial or extracranial arterial stenosis (as determined by angiography or CTA/MRA  $\leq$  6 months prior to index procedure) greater in severity than the lesion to be treated, cerebral aneurysm  $>$  5 mm, AVM (arteriovenous malformation) of the cerebral vasculature, or other abnormal angiographic findings.
2. Patient has a history of spontaneous intracranial hemorrhage within the past 12 months, or has had a recent (<7 days) stroke of sufficient size (on CT or MRI) to place him or her at risk of hemorrhagic conversion during the procedure (less than one-third middle cerebral artery volume).
3. Patient had hemorrhagic transformation of an ischemic stroke within the past 60 days.
4. Patient with a history of major stroke attributable to either carotid artery (CVA or retinal embolus) with major neurological deficit (NIHSS  $\geq$  5 OR mRS  $\geq$  3) likely to confound study endpoints within 1 month of index procedure.
5. Patient has an evolving stroke.
6. Patient has an intracranial tumor.

7. Patient has neurologic illnesses within the past two years characterized by fleeting or fixed neurologic deficit which cannot be distinguished from TIA or stroke, including but not limited to: moderate to severe dementia, partial or secondarily generalized seizures, complicated or classic migraine, tumor or other space-occupying brain lesions, subdural hematoma, cerebral contusion or other post-traumatic lesions, intracranial infection, demyelinating disease, or intracranial hemorrhage).
8. Patient has had a TIA or amaurosis fugax within 48 hrs prior to the procedure.
9. Patient has an isolated hemisphere defined as the ipsilateral middle cerebral artery being supplied only by the ipsilateral internal carotid artery.
10. Patient has active bleeding diathesis or coagulopathy or will refuse blood transfusion.
11. Patient had or will have CABG, endovascular stent procedure, valve intervention or vascular surgery within 30 days before or after the intervention.
12. Myocardial Infarction within 72 hours prior to the intervention.
13. Occlusion of the ipsilateral common or internal carotid artery.
14. An intraluminal filling defect (defined as an endoluminal lucency surrounded by contrast, seen in multiple angiographic projections, in the absence of angiographic evidence of calcification) whether or not it is associated with an ulcerated target lesion.
15. Patients with carotid string sign (a very high-grade carotid stenosis to the skull base with a long, thin, barely visible string of contrast within the true lumen of the artery.).
16. Ostium of Common Carotid Artery (CCA) requires revascularization (>50% stenosis).
17. Patient has an open stoma in the neck.
18. Patients with hostile necks due to prior neck irradiation
19. Female patients who are pregnant
20. Patient has history of intolerance or allergic reaction to any of the study medications or stent materials (refer to stent IFU), including aspirin (ASA), ticlopidine, clopidogrel, prasugrel, statin or contrast media (that can't be pre medicated). Patients must be able to tolerate statins and a combination of ASA and ticlopidine, ASA and clopidogrel or ASA and prasugrel.
21. Patient has a life expectancy <3 years with contingencies related to other medical, surgical, or interventional procedures as per the Wallaert Score and patients with primary, recurrent or metastatic malignancy who do not have independent assessment of life expectancy performed by the treating oncologist or an appropriate specialist other than the physician performing TCAR.
22. Patient has had a recent GI bleed that would interfere with antiplatelet therapy.
23. Patient is actively participating in an investigational drug or device trial (IND or IDE) that has not completed the required protocol follow-up period.
24. Patient has inability to understand and cooperate with study procedures.
25. Presence of extensive or diffuse atherosclerotic disease involving the proximal common carotid artery that would preclude the safe introduction of the study device.
26. Patient is otherwise unsuitable for intervention in the opinion of the physician.
27. Patients who cannot have MRI due to metallic implants (e.g. orthopedic implants, pacemakers, etc.)

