### 10.4.2 Procedural Medications

Heparin should be administered to achieve the desired activated clotting time (ACT). A sufficient dose should be given to achieve a target activated clotting time (ACT) of  $\geq 250$  seconds and maintained throughout the procedure.

At the discretion of the physician, procedural anticoagulation may be achieved with Angiomax (bivalirudin) which must be administered accordingly during the procedure.

The use of local or general anesthetic during the procedure is at the discretion of the physician.

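### Exclusion 2 is meant to keep out recent strokes large enough to bleed, but the only size it prints is an upper limit, so the threshold points the wrong way

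*Protocol*

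**What the plan says.** Section 8.3, item 2, has two limbs. The first concerns spontaneous intracranial hemorrhage in the past 12 months and is not in question. The second excludes a patient with a stroke less than 7 days old, described as a "stroke of sufficient size (on CT or MRI) to place him or her at risk of hemorrhagic conversion during the procedure". A parenthesis follows directly: "less than one-third middle cerebral artery volume".

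Section 8.1 makes the list binding: "If ANY of the exclusion criteria are met, the patient cannot be enrolled in this study or treated using the study devices".

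Section 8.2, item 1, accepts as symptomatic a patient of whom it says "the patient has a history of stroke (minor or non-disabling", along with TIA or amaurosis fugax, within 180 days of the procedure. It sets no minimum interval after the stroke.

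**The concern.** The words and the number in one criterion run in opposite directions. The words exclude strokes that are big enough to be dangerous. The number, placed where a reader expects the definition of big enough, describes strokes below a limit.

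Two errors could follow. A site that applies the number would reject a patient with a small infarct under 7 days old, whom section 8.2, item 1, would otherwise accept. A site that relies on the number alone would find nothing in item 2 against an infarct of one-third or more, which is the group the clause is meant to keep out.

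The second error matters more for safety. Section 10.4.2 calls for heparin to a target activated clotting time of at least 250 seconds throughout the procedure (bivalirudin is allowed instead), and section 10.3.1 calls for dual antiplatelet treatment beforehand. With up to 10 sites in the United States and up to 2 in the European Union, sites could also apply the criterion differently.

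**Working it through.** No sample size, power or error rate is involved, so there is nothing to recompute. The check compares the direction of the clause with that of the number, then looks for text elsewhere that settles the conflict.

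**Step 1: direction of each part.** A stroke of sufficient size to cause a risk is one at or above some size, which is a lower bound. A stroke of less than one-third of the territory is one below some size, which is an upper bound. One cannot define the other.

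**Step 2: what each reading does to an infarct under 7 days old.**

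| Reading of item 2 | Below one-third | One-third or more |
|---|---|---|
| Clause alone, parenthesis ignored | Physician's judgment | Physician's judgment; the larger the infarct, the more clearly excluded |
| Parenthesis defines the excluded size | Excluded | Not excluded by item 2 |
| Clause and parenthesis must both be met | Excluded if judged at risk | Not excluded by item 2 |
| Parenthesis describes strokes still allowed | Allowed | Excluded |

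Only the last reading gives a size rule that serves the stated purpose. It needs words that are not there, such as *except* or *permitted if*. The two readings that use the parenthesis as it stands reverse the rule.

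**Step 3: does anything else in the protocol correct the number?**

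- Section 8.3, item 3, concerns hemorrhagic transformation that has already occurred, within 60 days.
- Item 4 concerns major deficit (NIHSS of 5 or more, or mRS of 3 or more) within 1 month, qualified by whether it is likely to confound the endpoints. It rests on clinical deficit, not on infarct size.
- Item 5 concerns an evolving stroke.
- Item 8 sets a waiting period of 48 hours, but for TIA and amaurosis fugax only.
- Item 26 is the physician's general opinion on suitability.
- Appendix 4 grades stroke by NIHSS and Rankin score and gives no infarct volume.

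None of these states an infarct size. Item 2 is the only criterion meant to address size and future bleeding risk, and its number stands uncorrected.

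**Step 4: is this an artifact of the text?** The sentence is complete and grammatical, and nothing suggests redaction or a reading fault.

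**The case against.** The strongest reply is that the operative test is the clause. A large recent infarct meets it whatever the parenthesis says, and it is unnatural to let a parenthesis cancel the sentence it sits in. A fair-minded reader may take it to describe strokes that remain acceptable.

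The group at risk is also nearly empty by other rules. The asymptomatic route requires 180 days without neurological symptoms, so a patient with a clinical stroke in the past week must enter as symptomatic. If that stroke is the qualifying event, it must be minor or non-disabling. Items 3, 4, 5 and 26 remove many of the rest. For harm to follow, a patient would need a large infarct with little deficit and a physician who disregards both the clause and item 26.

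Exclusions also exist to narrow inclusions, so barring some minor strokes in the first 7 days of a 180-day window is not in itself a contradiction. Finally, this is a descriptive single-arm study of 50 to 75 patients with no formal hypothesis test, and it adds only imaging to a routine procedure.

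Most of this stands, and it limits the consequence. It is right that the overlap with the inclusion criterion, taken alone, proves nothing about item 2. The reply does not rescue the number. The charitable reading leads to the same rule as the correction proposed here, so it confirms that the printed wording fails to say what is meant.

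**Conclusion.** The criterion is wrong as written: its only size threshold contradicts the clause it qualifies, and nothing elsewhere in the protocol repairs it. The practical effect is minor. The number of candidates with a stroke within 7 days is not given and is probably small among those who pass the other criteria. The likelier mistake is the needless exclusion of small infarcts, not the treatment of large ones. No endpoint estimate or other statistical figure depends on it.

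The conclusion assumes that the clause expresses the intent, so that larger infarcts are the ones to keep out. The clause itself says so. That one-third is the intended cut-off is inferred from the parenthesis and needs clinical confirmation. The point should be corrected because the criterion is binding and concerns safety.

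**What to change.** Replace the parenthesis in section 8.3, item 2, with *one-third or more of the middle cerebral artery volume*, or state outright that only infarcts below one-third are permitted. The two give the same size rule. The sponsor's clinical lead should confirm the cut-off. If no cut-off is wanted, deleting the parenthesis would also remove the contradiction, but would leave the decision wholly to judgment.

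Use the same wording on any eligibility form and send sites a short note. The cost is one phrase and that note; no analysis, sample size or schedule changes.
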